9.6 Serious Adverse Event and Suspected Unexpected Serious Adverse Reaction Reporting

Information on suspected unexpected serious adverse reactions (SUSARs) will be distributed to the relevant regulatory agencies, health authorities, institutional review board (IRB)/independent ethics committee (IEC), and investigational sites.

9.6.1 Investigator Reporting to the Sponsor

All SAEs that occur after the ICF is signed and up to 90 days after administration of the last dose of study drug must be recorded in the AE eCRF within 24 hours of knowledge of the occurrence (this refers to any AE that meets any of the criteria in [Section 9.1.1](#), regardless if it is considered related to study drug). SAEs occurring more than 90 days after the last dose of study drug must be reported only if assessed as related to study drug.

To report the SAE, the Investigator must record the relevant information in the AE eCRF and any other applicable information in the relevant eCRF (eg, drug dispensation eCRF, applicable laboratory eCRF). If the event meets serious criteria and it is not possible for the site to access the EDC system, the site must complete the paper SAE reporting form and email or fax it to ICON Safety using the email or fax number listed in Table 8, all within 24 hours of awareness. When the EDC system becomes available, the site must enter the SAE information into the EDC, exactly as it was recorded on the paper SAE reporting form, within 24 hours of the system becoming available.

For all SAEs, the Investigator is obligated to obtain and provide information to the Sponsor and ICON Safety in accordance with the time frames for reporting specified above. In addition, an Investigator may be requested by the Sponsor to obtain specific additional follow-up information in an expedited fashion. This information may be more detailed than that captured in the AE eCRF or back-up paper SAE form. In general, this will include a description of the AE in sufficient detail to allow for a complete medical assessment of the case and an independent determination of possible causality. Information on other possible causes of the event, such as concomitant medications and illnesses, must be provided. In the case of a subject death, a death certificate and summary of available autopsy findings (as applicable) must be submitted as soon as possible to the Sponsor or its designee.

9.6.2 Serious Adverse Event Follow-up

The Investigator must continue to follow the subject until the SAE has subsided; until the condition becomes chronic in nature or stabilizes (in the case of persistent impairment); until the subject withdraws consent, is lost to follow-up, or dies; or until it has been assessed that study treatment/procedure is not the cause of the SAEs.

9.6.3 Reporting to Regulatory Agencies and Institutional Review Boards/Independent Ethics Committees

The Sponsor will report all relevant information about SUSARs that are fatal or life-threatening as soon as possible to applicable health authorities and the central IRB/IEC and in any case no later than 7 days after knowledge by the Sponsor of such a case. After the initial 7-day SUSAR notification, a final 15-day SUSAR notification will be submitted (ie, 8 days after the initial 7-day notification).

All other SUSARs will be reported to the FDA, competent authorities in all the countries concerned, and the central IRB/IEC, as applicable, as soon as possible but no later than 15 days after first knowledge by the Sponsor.

The Sponsor will inform all Investigators in accordance with applicable regulatory requirements, with instructions to submit to local IRBs/IECs in accordance with applicable requirements.

9.7 Rapid Notification of Adverse Events of Special Interest

In addition to SAEs, the following AESIs will be recorded in the AE eCRF within 24 hours of site awareness irrespective of seriousness, severity, or causality:

- IRRs \geq Grade 2
- Any potential Hy's Law case ($>3 \times$ ULN of either ALT/AST with concurrent $>2 \times$ ULN of total bilirubin and lack of alternate etiology)
- Any irAEs defined as AEs requiring the use of systemic corticosteroids (or other immune-suppressive therapy) within 30 days after the AE onset date with no clear alternative etiology, or requiring the use of systemic hormonal supplementation. Examples may include, but are not limited to:
 - Pneumonitis
 - Colitis
 - Hepatitis (including AST or ALT elevations $>3 \times$ ULN or bilirubin $>1.5 \times$ ULN)
 - Nephritis (including serum creatinine $>1.5 \times$ ULN)
 - Pancreatitis
 - Motor and sensory neuropathy (including Guillain-Barré syndrome and myasthenia gravis)
 - Myocarditis
 - Encephalitis or meningoencephalitis
 - Endocrinopathies (including but not limited to hypothyroidism, hyperthyroidism, hypophysitis, diabetes mellitus, and adrenal insufficiency)
 - Ocular toxicities (eg, uveitis)
 - Skin reactions including Stevens-Johnson syndrome or toxic epidermal necrolysis
 - Diarrhea

Refer to [Section 9.6](#) and [REDACTED] for reporting SAEs and AESIs.

9.8 Module-specified Events

Subjects with advanced cancer enrolling in this study who have received prior treatment may have some degree of bone marrow suppression from prior therapy and/or laboratory abnormalities due to underlying disease status. Only changes in the grade of baseline laboratory values that require intervention (eg, transfusions, delay in study treatment administration) should be reported as AEs.

For this protocol, disease progression is an efficacy endpoint and in and of itself is not considered an AE or SAE unless disease progression results in death. Death that occurs during the AE reporting period (as defined above) that is attributed solely to disease progression of the condition will be recorded in the AE eCRF as a Grade 5 AE (regardless of attribution to study

treatment). Deaths reported as SAEs due to progressive disease and considered not related to study treatment will be excluded from TEAE analysis.

10 STATISTICAL METHODS AND CONSIDERATIONS

1. **What is the primary purpose of the study?** (Please check one box)

A high-contrast, black and white image showing a dark, textured surface on the left and a bright, textured surface on the right, separated by a horizontal line.

This figure displays a sequence of 8 frames showing the progression of a black cross shape being filled in. The top row shows the cross in various stages of being filled in with black pixels. The bottom row shows the cross with a solid black vertical bar on the left and a solid black horizontal bar on the right, with a small white gap between them. The last frame in the sequence has a vertical line to its right.

10.2 Statistical Analyses

Analyses will be conducted by cohort and may be conducted overall. Statistical assessments/methods for safety, efficacy, PK/pharmacodynamics (PD), and immunogenicity are found in the Core ([Appendix A](#)). Additional endpoints will include, but are not limited to, the following endpoints: frequency of AESIs and percentage of reduction in tumor burden.

For Part B1, the proportion of subjects with pCR, major pathologic response/near pCR, and pPR will be summarized by count and percentage using the safety analysis population. In addition, a 95% CI based on the method of Koyama and Chen ([Koyama 2008](#)) will be provided. This method is appropriate because it is proposed for Simon's 2-stage design, accounting for the inherent futility analysis. Subjects who, after neoadjuvant therapy, are deemed by the Investigator to be ineligible for surgery due to progression or toxicity will be considered as non-responders.

RFS, assessed in subjects who undergo surgical resection, is defined as the time from resection until the date of the first recurrence (local, regional, or distant metastasis), new primary melanoma, or death from any cause, whichever occurs first ([Weber 2017](#)). A subject who dies without reported recurrence will be considered to have recurred on the date of death. For subjects who remain alive and whose disease has not recurred, RFS will be censored on the date of last disease assessment. For those subjects who remain alive and have no recorded postsurgery disease assessment, RFS will be censored on the day of surgery. Censoring rules for the analysis of RFS are presented in Table 10. RFS curves, RFS medians with 95% CIs, and RFS rates at 6, 12, 18, 24, and 36 months with 95% CIs will be estimated using Kaplan-Meier methodology and may be stratified by PD-L1 status and/or disease stage.

Table 10 Censoring Scheme for Relapse-free Survival

Scenario	Date of Event of Censoring	Outcome
Recurrence (local, regional, distant, new primary melanoma)	Date of first recurrence	Event
Death without recurrence	Date of death	Event
Disease at baseline	Date of surgery	Event
No postsurgery disease assessment	Date of surgery	Censored
No postsurgery disease assessments and no death	Date of surgery	Censored
No recurrence and no death	Date of last disease assessment	Censored
New anticancer therapy, tumor-directed radiotherapy, or tumor-directed surgery received without recurrence reported prior to or on the same day of disease assessment	Date of last disease assessment prior to or on the same date of initiation of subsequent therapy	Censored
Second non-melanoma primary cancer reported prior or on the same day of disease assessment	Date of last disease assessment prior to or on the same date of diagnosis of second nonmelanoma primary cancer	Censored

A separate statistical analysis plan (SAP) will be generated and additional details will be specified within the SAP. In instances where the SAP might contradict the analyses specified in this Module [REDACTED], the SAP supersedes the Module [REDACTED].

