5.2 Study Drug Administration and Dosing Regimen

5.2.1 Study Drug Administration

5.2.2 Study Treatment Dosing Regimen

CX-072 and ipilimumab are to be administered in this study as follows:

- Part A:
 - Combination treatment: 800 mg CX-072 + 3 mg/kg ipilimumab, q3w
 - Monotherapy treatment: 800 mg CX-072, q2w
- Part B:
 - Combination treatment: 800 mg CX-072 + 1 mg/kg ipilimumab, q3w
 - Monotherapy treatment: 800 mg CX-072, q2w

In Part A, subjects will be treated with 4 doses of 800 mg CX-072 IV plus 3 mg/kg ipilimumab IV combination therapy (ie, q3w on Cycle 1 Day 1, Cycle 1 Day 22, Cycle 2 Day 1 [Study Day 43], and Cycle 2 Day 22 [Study Day 64]; all ± 2 days). Three weeks following receipt of the fourth dose of combination treatment (ie, Study Day 85 [± 2 days]), subjects will receive 800 mg CX-072 IV monotherapy q2w until the occurrence of progressive disease by irRECIST, unacceptable toxicity, or the subject meets any other criterion for treatment discontinuation (Section 4.11).

In Part B, subjects will be treated with 2 doses of 800 mg CX-072 IV plus 1 mg/kg ipilimumab IV combination (ie, q3w on Cycle 1 Day 1, Cycle 1 Day 22; all ± 2 days) followed by surgical resection of the tumor on Day 43 (-2/+7 days). An additional 2 doses of 800 mg CX-072 IV plus 1 mg/kg ipilimumab IV combination will be administered approximately 6 weeks postsurgery (ie, q3w on Cycle 2 Day 1 [Study Day 85 (± 2 days)] and Cycle 2 Day 22 [Study Day 106 (± 2 days)]). Three weeks following receipt of the fourth dose of combination treatment (ie, Study Day 127 [± 2 days]), subjects will have the option to continue with 800 mg CX-072 IV monotherapy q2w following discussion and agreement of risk/benefit between the Investigator and the Sponsor Medical Monitor. Subjects may receive up to 1 year of CX-072 infusions postsurgery (including 2 postsurgery combination doses and then as monotherapy) until the occurrence of disease relapse, unacceptable toxicity, or the subject meets any other criterion for treatment discontinuation ([Section 4.11](#)).

A maximum of 4 doses of ipilimumab may be administered to any subject (Parts A and B).

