6.2 Part B

- The primary criterion for defining evidence of anticancer activity is pathologic response based on central review of tumor sample from surgical resection. The criteria for management of subject care and treatment discontinuation are radiographic response assessment (prior to surgery), local pathologic assessment of surgical sample after surgery, or disease relapse. Tumor response, as defined by RECIST v1.1, will be assessed prior to surgical resection; however, responses will not be confirmed because the tumor assessment will be followed by surgical resection.
- Pathologic analysis of the resected tumor will be conducted by central review and according to the International Neoadjuvant Melanoma Consortium (INMC) scoring system ([Tetzlaff 2018](#))
 - Pathologic complete response (pCR): Complete absence of viable tumor
 - Major pathologic response/near pCR: >0% but <10% of viable tumor in the treated tumor bed
 - Pathologic partial response (pPR): ≤50% of the treated tumor bed is occupied by viable tumor cells
 - Pathologic nonresponse (pNR): >50% of the tumor bed occupied by viable tumor cells
- Relapse is defined as the recurrence of melanoma locally, regionally, with distant metastasis, or with a new primary lesion
- Tumor assessments will be completed by CT or MRI at Screening, prior to scheduled surgical resection (ie, Cycle 1 Day 40 ±2 days), after completion of combination treatment following surgery (ie, Cycle 2 Day 22 [Study Day 106] ±2 days), and then every 12 (±1) weeks until relapse. After 3 years, tumor assessments will be performed according to standard of care.
- Prior to surgical resection, responses noted at the time of the tumor assessment will not be confirmed by a subsequent tumor assessment because the subject will undergo surgery following the presurgical tumor assessment

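### One row of Table 10 censors at surgery any subject never assessed after surgery, including one who has died, and so contradicts the death row and the Section 10.2 text

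*Combined protocol and SAP*

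**What the plan says.** Section 10.2 assesses RFS in Part B subjects who undergo resection, measures it from resection, and counts any death as an event. Two sentences of the text bear on a subject with no assessment after surgery:

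- "A subject who dies without reported recurrence will be considered to have recurred on the date of death". No postsurgery assessment is required.
- "For those subjects who remain alive and have no recorded postsurgery disease assessment, RFS will be censored on the day of surgery". This applies to survivors only.

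The text then points to the table: "Censoring rules for the analysis of RFS are presented in Table 10". Three rows of Table 10 matter here:

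- The row for death with no recurrence: event, at the date of death.
- "No postsurgery disease assessment": censored, at the date of surgery.
- "No postsurgery disease assessments and no death": censored, at the date of surgery.

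Neither the table nor the text says which row applies when a subject meets more than one. On later detail, Section 10.2 says: "A separate statistical analysis plan (SAP) will be generated and additional details will be specified within the SAP". It adds that the SAP prevails where the two differ.

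**The concern.** The two censoring rows are nearly identical and lead to the same date and outcome, but only the second excludes subjects who have died. The first may be a leftover duplicate. As written, it also covers a resected subject who dies before any postsurgery assessment, and it turns that subject's event into censoring at time zero.

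Such censoring would be caused by the event itself. The death disappears, the subject leaves the risk set before the curve starts, and the Kaplan-Meier estimate is too high. The error can go in one direction only. RFS is a named secondary endpoint of Part B, with rates planned at 6, 12, 18, 24 and 36 months. The primary pathologic response analysis is not touched.

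**Working it through.** **Rule check.** Take resected subjects with no recorded recurrence and compare the table with the text.

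| Vital status | Assessed after surgery | Table 10 | Section 10.2 text |
|---|---|---|---|
| Alive | Yes | Censored at last assessment | Same |
| Alive | No | Censored at surgery (both near-identical rows) | Same |
| Died | Yes | Event at death | Same |
| Died | No | Event at death (death row) **and** censored at surgery (unconditional row) | Event at death |

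Only the last line conflicts. If the unconditional row is removed, that subject meets the death row alone. The living unassessed subject is still censored at surgery by the row that carries the no-death condition.

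**Can it happen?** Section 5.2.2 puts surgery on Day 43 (-2/+7 days). Section 6.2 puts the first scheduled postsurgery scan on Day 106 (±2 days).

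- Nominal gap: 106 − 43 = 63 days
- Shortest: (106 − 2) − (43 + 7) = 54 days
- Longest: (106 + 2) − (43 − 2) = 67 days

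The exposed period is longer for anyone never assessed. It could be shorter if assessments other than imaging count, which cannot be checked because the Part B schedule is unreadable in the available copy.

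**Size if the row were applied.** The plan states no figure to reproduce. Let N be the number resected, with one early unassessed death, k recurrences by time t, and no other censoring before t.

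- Death counted: RFS = (N − 1 − k)/N
- Death censored at time zero: RFS = (N − 1 − k)/(N − 1) = S(t), the RFS in the other subjects
- Difference: S(t) − S(t)(N − 1)/N = S(t)/N

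For N, Section 3.3 gives 14 subjects in Stage 1 and about 40 in total (range 38 to 48). This assumes that every enrolled subject is resected. For S(t), the ceiling is 1 (no other events). As an assumption, the 12- and 18-month rates of the adjuvant pembrolizumab study quoted in Section 1.2.1 are also used: 75.4% and 71.4%.

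| N | Ceiling, 1/N | S = 0.754 | S = 0.714 |
|---|---|---|---|
| 14 | 7.1 points | 0.754/14 = 5.4 | 0.714/14 = 5.1 |
| 38 | 2.6 | 0.754/38 = 2.0 | 0.714/38 = 1.9 |
| 40 | 2.5 | 0.754/40 = 1.9 | 0.714/40 = 1.8 |
| 48 | 2.1 | 0.754/48 = 1.6 | 0.714/48 = 1.5 |

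**Whole-count check, N = 40 and 10 recurrences by 12 months.**

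- One such death: 29/40 = 72.5% if counted, 29/39 = 74.4% if censored at surgery, a difference of 1.9 points.
- Two such deaths: 28/40 = 70.0% against 28/38 = 73.7%, a difference of 3.7 points.

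**The case against.** The strongest reply is that the plan already states the right rule five times: in the RFS definition, in the two sentences of text, in the death row, and in the row limited to survivors. One row lacks a qualifier, which makes this a wording slip. Harm needs both a death before any assessment and a programmer who follows the stray row against everything around it. The documents give no expected number of such deaths.

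The shift is also small beside sampling error. At S = 0.754 the binomial standard error is √(0.754 × 0.246/40) = 6.8 points for N = 40, and 11.5 points for N = 14. No test or decision rule in the visible text depends on RFS.

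Such a death would be hard to miss. Serious events are collected for 90 days after the last dose (Section 9.6.1). Counted from the second presurgery dose on Day 22, that runs to Day 112, past the Day 106 scan. Overall survival is also a Part B objective in Section 2.2.1. Finally, the SAP, which prevails over this document, and the Core, which holds efficacy methods, were not available.

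All of this limits the likelihood and the weight of the problem, and it is accepted. It does not remove the contradiction. The text itself sends the reader to Table 10 for the censoring rules. If the death row is taken to win, the unconditional row adds nothing. If it does not win, a defined event is lost. Neither reading is a reason to keep the row. An SAP that has not been seen could correct it or copy it.

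**Conclusion.** The concern holds. Table 10 contradicts itself and the Section 10.2 text for a resected subject who dies with no recorded recurrence and no postsurgery assessment. Confidence in the contradiction is high. Confidence that it would reach the analysis is low, because the intended reading is plain and the SAP is unseen.

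If the row were applied, the bias would always favor the treatment. Per death it would be up to 2.5 points at 40 resected subjects and 7.1 points at 14, or about 1.9 and 5.4 points at the assumed 12-month rate. These figures are illustrations. They rest on every enrolled subject being resected, no other censoring before the time point, and an RFS rate borrowed from another study. The point should be fixed, but it is limited to a secondary endpoint.

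**What to change.** Delete the row "No postsurgery disease assessment" from Table 10 and keep "No postsurgery disease assessments and no death". Add one sentence under the table saying that a recurrence or death takes precedence over censoring for missing assessments. Write the same rule into the SAP before any RFS data are analyzed, so that it is not settled once the deaths are known.

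Adding the missing no-death condition to the first row would also remove the contradiction, but it would leave two identical rows. The proposed sentence covers missing assessments only. How events rank against the rows for new anticancer therapy and second nonmelanoma cancers is a separate matter that the SAP can settle.

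The cost is one deleted row and one added sentence. Data collection, sample size and the primary analysis do not change. Reported RFS would be slightly lower only if such deaths occur and the row would otherwise have been applied.

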11 INVESTIGATOR REQUIREMENTS AND QUALITY CONTROL

11.1 Ethical Conduct of the Study

This study will be conducted in accordance with the current clinical protocol as approved by the applicable IRB/IEC, ICH Good Clinical Practice Guidelines, and other applicable regulatory requirements.

11.2 Institutional Review Board/Independent Ethics Committee

The IRB/IEC will meet all applicable regulatory requirements governing IRBs.

The Investigator will provide the Sponsor or its designee with documentation of IRB/IEC approval of the following documents before the study begins at the study site(s) managed by the Investigator: Module, Core, ICF, and any other relevant materials intended for or directed to subjects (eg, subject diaries, advertisements). The Investigator will supply the Sponsor with documentation of IRB/IEC requirements regarding continuing review and approval of revisions to any of these documents.

11.3 Subject Information and Informed Consent

Written informed consent using the ICF is required from each subject prior to any testing under this Module, including screening tests and evaluations. The ICF, as specified by the clinical site's IRB/IEC, must follow applicable regulatory requirements for the protection of human subjects.

The ICF will be used to explain the risks and benefits of study participation in simple terms before the subject will be entered into the study. The ICF will contain a statement that the consent is freely given, that the subject is aware of the risks and benefits of entering the study, and that the subject is free to withdraw from the study at any time. Written informed consent must be given by the subject after receipt of detailed information on the study. It is the responsibility of the Investigator to obtain consent and to provide the subject with a copy of the signed and dated ICF. Confirmation of a subject's informed consent must also be documented in the subject's medical record prior to any procedures performed under this protocol, including screening tests and evaluations.

All ICFs used for this Module must be approved by the appropriate IRB/IEC and by the Sponsor or its designee. The ICF must not be altered without the prior agreement of the relevant IRB/IEC and the Sponsor.

12 STUDY ADMINISTRATIVE INFORMATION

12.1 Core or Module Amendments

Changes to the conduct of the study will be prepared by the Sponsor as an amendment to this Module [REDACTED] and will be implemented only upon joint approval of the Sponsor or its designee and the Investigator(s). Amendments should also receive written IRB/IEC approval prior to implementation, except when necessary to eliminate immediate hazards to the subjects or when the changes involve only logistical or administrative aspects of the study (eg, change of monitor, telephone numbers). In this case, the Sponsor will amend and implement the change(s) and will subsequently notify the regulatory authorities and/or the IRB/IEC, as appropriate.

